7.1.2. Schedule of Study Procedures

Table 1: Schedule of Study Procedures-Screening to Month 12 (Table 1 of 2)

	Screening Visits		Day 0	M 1	M 3	1-Month Post-Titration Visit ^b	M 6	M 9	M 12
	1	2 ^a							
Visit Windows (+/-)^c	3 to 8 wk prior to Day 0	1 to 6 wk prior to Day 0		+1 wk	±2 wk	±1 wk	±2 wk	±2 wk	±2 wk
Informed Consent	X								
Medical/PBC History ^d	X								
Cirrhosis Status Assessment ^e	X								
Inclusion/Exclusion Criteria	X	X	X						
Physical Exam	X			X		X	X		X ^d
Assessments for Mayo Risk Score ^f	X						X		X
Assessments for Child-Pugh Score ^g	X				X		X	X	X
Vital Signs (including weight)	X ^h		X		X		X	X	X ^h
12-Lead Electrocardiogram	X								X
Subject Questionnaires (5-D Pruritus Scale and Pruritus VAS)			X				X		X
Quality of Life Questionnaires (PBC-40, EQ-5D-5L, and FIS) ⁱ			X						X
Fibroscan [®] TE ^j			X				X		X
DEXA ^k			X						X
Endoscopy ^l			X						X
Hepatic Ultrasound ^m		X					X		X
Adverse Events	X	X	X	X	X	X	X	X	X
Prior and Concomitant Medications	X	X	X	X	X	X	X	X	X
Health Outcome Assessments ⁿ			X		X		X	X	X

Table 1: Schedule of Study Procedures-Screening to Month 12 (Table 1 of 2) (Continued)

	Screening Visits		Day 0	M 1	M 3	1-Month Post-Titration Visit ^b	M 6	M 9	M 12
	1	2 ^a							
Visit Windows (+/-)^c	3 to 8 wk prior to Day 0	1 to 6 wk prior to Day 0		+1 wk	±2 wk	±1 wk	±2 wk	±2 wk	±2 wk
Randomization/Treatment Assigned			X						
Dose Titration: Standard Dosing ^{o,p}					X		X (if applicable)		
Dose Titration: Modified Dosing (if applicable) ^{o,p}					X		X	X	X
Dispense Investigational Product ^q			X		X		X	X	X
IP Accountability/Compliance				X	X	X	X	X	X
Dosing Diary			X	X	X	X	X	X	X
LABORATORY EVALUATIONS^r									
Urinalysis	X		X						X
Urine-based β-hCG Pregnancy Test ^s	X		X						
Chemistry/Hematology/Coagulation	X	X ^a	X	X	X	X	X	X	X
OCA, C4, and FGF-19 (plasma)			X		X		X	X ^t	X
Markers of Hepatic Fibrosis and/or Inflammation ^u			X				X		X
Genetics ^v			X						X
Blood Sample for Future Analysis ^w			X				X		X

AE = adverse event; β-hCG = beta human chorionic gonadotropin; DEXA = dual-emission X-ray absorptiometry; EOS= End of Study; EOT = End of Treatment; FGF-19 = fibroblast growth factor-19; FIS = Fatigue Impact Scale; IP = Investigational Product; M = month, TE = transient elastography; VAS = Visual Analogue Scale; wk = week

^a All subjects will have the chemistry panel retested to ensure subjects have two ALP and bilirubin assessments at least 2 weeks apart to calculate the mean result for both analytes. The mean of all screening ALP and bilirubin assessments will be used to determine eligibility. Samples for hematology and coagulation will not be collected at Screening Visit 2.

^b Post-Titration visits must be performed 1 month (+ 1 week) after any up-titration in dose and/or frequency in subjects following modified dosing due to Child-Pugh B and Child-Pugh C hepatic impairment. In subjects following the standard dosing regimen, the post-titration visit must be performed only after the first up-titration to 10 mg OCA or matching placebo, or after ≥3 months at a decreased dose or frequency.

^c Visits should be based on Day 0 (not on the prior visit) with the exception of the Post-Titration Visit, which is based on the date of titration.

- ^d Medical history at Screening and the yearly physical exam will include an assessment of smoking and alcohol consumption history and current habits for both.
- ^e Presence or absence of cirrhosis should be assessed per [Section 9.7.3](#). Cirrhosis status should be repeated as clinically indicated.
- ^f Mayo Risk Score will be calculated based on central laboratory evaluations, diuretic use data, and peripheral edema assessment data captured in the eCRF.
- ^g Child-Pugh Score will be calculated based on ascites assessment, hepatic encephalopathy grade, and central laboratory evaluations per the Child-Pugh scoring system noted in the eCRF.
- ^h Height will be collected at this visit.
- ⁱ The EQ-5D-5L and FIS Quality of Life questionnaires are validated for use in multiple languages. If a validated translation is not available in the local language required for a specific study subject, the data from that questionnaire will not be collected (See [Section 11.1.2.2](#) and [Section 12.2.6](#)).
- ^j Transient elastography (TE) will be conducted at 6-month intervals at all study sites where the Fibroscan[®] TE device is available. Please refer to [Section 9.7.7](#) for additional information related to the allowed windows at Day 0 for this procedure.
- ^k DEXA will be conducted at 12-month intervals at all study sites where the DEXA device is available. Please refer to [Section 9.7.7](#) for additional information related to the allowed windows at Day 0 for this procedure.
- ^l Endoscopy will be conducted at selected study sites where the device is available to assess for the presence of oesophageal varix/varices. Please refer to [Section 9.7.7](#) for additional information related to the allowed window at Day 0 for this specific procedure.
- ^m Ultrasound will be conducted to enhance HCC surveillance. For all on study (eg, post-Day 0) ultrasounds: unless HCC has already confirmed by biopsy, a second confirmatory image (eg, MRI) should be obtained to confirm if a study endpoint has been met.
- ⁿ Health Outcome Assessments: Data related to non-study related medical or surgical treatment procedures that the subject underwent and any medically relevant health care provider (HCP) or non-HCP related office visits that the subject attended should be collected throughout the study.
- ^o Pre-titration tolerability assessment, which include a review of AEs and a review of safety laboratory results (eg, chemistry, hematology, and coagulation), must be completed by the Investigator before any up-titration can occur as defined in [Section 7.4.1](#). Lab results obtained within 2 months prior to any up-titration may be used for assessment.
- ^p Dose Titration is based on cirrhosis status ([Section 9.7.3](#)) and Child-Pugh Score ([Section 9.7.4](#)). The initial dose titration of investigational product may occur at the Month 3 visit, or any study visit thereafter for subjects on all dosing regimens, based on tolerability and biochemical response. Subsequent dose titration(s) for subjects who are classified as Child-Pugh B or Child-Pugh C and following a modified dosing schedule may occur no earlier than 6 weeks after the previous dose titration. For complete modified dose titration criteria, refer to [Appendix A](#).
- ^q Subjects will be instructed to begin dosing on the day after the Day 0 visit (ie, on Day 1) and to take investigational product at approximately the same time of day. Subjects must be instructed to swallow the tablet whole; they must not chew, divide, or crush the tablet.
- ^r The subject should be instructed to fast overnight (at least 8 hours) prior to each visit. Fasting is required prior to all study visits (except Screening Visit 1) but water is permitted.
- ^s Urine β -hCG pregnancy tests must be performed in females of childbearing potential prior to entry. If positive, a confirmatory blood test must be performed at the central laboratory. If the blood test is also positive, the subject may not be enrolled in the study. (Additional testing may be conducted where required, regionally).
- ^t Only OCA PK samples will be collected at Month 9 at select study sites in a subset of subjects. Please refer to [Section 9.7.13](#) for the PK sampling schedule.
- ^u Markers of hepatic fibrosis and/or inflammation are defined in [Section 11.1.2](#).
- ^v A genetics study will be conducted in a subset of subjects who provide consent for analyses of these samples. Genetics samples will be collected at Day 0 and every other year beginning at Month 12. If a baseline (e.g. Day 0) genetic sample is not obtained, subsequent genetic samples are not required to be collected during the course of the study.
- ^w Please refer to [Section 11.1.2.3](#) for description of the blood sample to be collected for future analysis.

Table 2: Schedule of Study Procedures-Year 2 Through End of Study (Table 2 of 2)

	Year 2 through End of Study					
	M 3 continued follow-up	1-Month Post- Titration Visit ^a (if applicable)	M 6 continued follow-up	M 9 continued follow-up	M 12 continued follow-up	EOT/ EOS ^b
Visit Windows (+/-) ^c	±2 wk	+1 wk	±2 wk	±2 wk	±2 wk	±2 wk
Physical Exam ^d		X			X	X
Assessment for Mayo Risk Score ^e			X		X	X
Assessments for Child-Pugh Scores ^f	X		X	X	X	X
Vital Signs (including weight)			X		X ^g	X ^g
12-Lead Electrocardiogram					X	X
Subject Questionnaires (5-D Pruritus Scale and Pruritus VAS)			X		X	X
Quality of Life Questionnaires (PBC-40, EQ-5D-5L, and FIS) ^h					X	X
Fibroscan [®] TE ⁱ			X		X	X
DEXA ^j					X	X
Endoscopy ^k					X	
Hepatic Ultrasound ^l			X		X	X
Adverse Events	X	X	X	X	X	X
Prior and Concomitant Medications	X	X	X	X	X	X
Health Outcome Assessments ^m	X		X	X	X	X
Dose Titration (if applicable) ^{n,o}	X		X	X	X	
Dispense Investigational Product	X		X	X	X	
IP Accountability/Compliance	X	X	X	X	X	X
Dosing Diary	X	X	X	X	X	X
LABORATORY EVALUATIONS^p						
Urinalysis					X	X
Chemistry/Hematology/Coagulation	X	X	X	X	X	X

Table 2: Schedule of Study Procedures-Year 2 Through End of Study (Table 2 of 2) (Continued)

	Year 2 through End of Study					
OCA, C4, and FGF-19 (plasma)					X	X
Markers of Hepatic Fibrosis and/or Inflammation ^q			X		X	X
Genetics ^r					X	
Blood Sample for Future Analysis ^s			X		X	X

AE = adverse event; β -hCG = beta human chorionic gonadotropin; DEXA = dual-emission X-ray absorptiometry; EOS= End of Study; EOT = End of Treatment; FGF-19 = fibroblast growth factor-19; FIS = Fatigue Impact Scale; IP = Investigational Product; M = month, TE = transient elastography; VAS = Visual Analogue Scale; wk = week

- ^a In subjects following the standard dosing regimen, the post-titration visit must be performed only after the first up-titration to 10 mg OCA or matching placebo, or after ≥ 3 months at a decreased dose or frequency. Post-titration visits must be performed 1 month \pm 1 week after any up-titration in dose and/or frequency in subjects following modified dosing due to Child-Pugh B and Child-Pugh C hepatic impairment.
- ^b As soon as possible upon study discontinuation and as near as possible to last dose taken.
- ^c Visits should be based on Day 0 (not on the prior visit) with the exception of the Post-Titration Visit, which is based on the date of titration.
- ^d The yearly physical exam will include an assessment of smoking and alcohol consumption history and current habits for both.
- ^e Mayo Risk Score will be calculated based on central laboratory evaluations, diuretic use data, and peripheral edema assessment data captured in the CRF.
- ^f Child-Pugh Score will be calculated based on ascites assessment, hepatic encephalopathy grade, and central laboratory evaluations per the Child-Pugh scoring system noted in the case report form.
- ^g Height will be collected at this visit.
- ^h The EQ-5D-5L and FIS Quality of Life questionnaires are validated for use in multiple languages. If a validated translation is not available in the local language required for a specific study subject, the data from that questionnaire will not be collected (See [Section 11.1.2.2](#) and [Section 12.2.6](#)).
- ⁱ Transient elastography (TE) will be conducted at 6-month intervals at all study sites where the Fibroscan® TE device is available. Not required if done within 3 months of visit
- ^j DEXA will be conducted at 12-month intervals at all study sites where the DEXA device is available. Not required if done within 6 months of visit.
- ^k Endoscopy will be conducted at all study sites where the device is available to assess for the presence of oesophageal varix/varices.
- ^l Ultrasound will be conducted to enhance HCC surveillance. For all on study (e.g. post-day 0) ultrasounds: unless HCC has already been confirmed by biopsy, a second confirmatory image (eg, MRI) should be obtained to confirm if a study endpoint has been met.
- ^m Health Outcome Assessments: Data related to non-study related medical or surgical treatment procedures that the subject underwent and any medically relevant health care provider (HCP) or non-HCP related office visits that the subject attended should be collected throughout the study.
- ⁿ Pre-titration tolerability assessment, which include a review of AEs and a review of safety laboratory results (eg, chemistry, hematology, and coagulation), must be completed by the Investigator before any up-titration can occur as defined in [Section 7.4.1](#). Lab results obtained within 2 months prior to any up-titration may be used for assessment.
- ^o Dose Titration is based on cirrhosis status (see [Section 9.7.3](#)) and Child-Pugh Score ([Section 9.7.4](#)). The initial dose titration of investigational products may occur at the Month 3 visit, or any study visit thereafter for subjects on all dosing regimens, based on tolerability and biochemical response. Subsequent dose titration(s) for subjects who are classified as Child-Pugh B or Child-Pugh C and following a modified dosing schedule may occur no earlier than 6 weeks after the previous dose titration. For complete modified dose titration criteria, refer to [Appendix A](#).
- ^p The subject should be instructed to fast overnight (at least 8 hours) prior to each visit. Fasting is required prior to all study visits, but water is permitted.
- ^q Markers of hepatic fibrosis and/or inflammation are defined in [Section 11.1.2](#).
- ^r A genetics study will be conducted in a subset of subjects who provide consent for analyses of these samples. Genetics samples will be collected at Day 0 and every other year beginning at Month 12.
- ^s Please refer to [Section 11.1.2.3](#) for description of the blood sample to be collected for future analysis.

7.1.3. Study Duration

The study is event driven and total duration will be determined by the time required to accrue approximately 127 primary endpoint events, estimated to be approximately 10 years. Subjects are expected to have a minimum follow-up time of approximately 6 years.

7.2. Number of Subjects

It is expected that approximately 428 subjects will be randomized in the study to achieve 127 adjudicated primary endpoint events.

7.3. Planned Dosing Regimen

Subjects will be randomized to treatment with either OCA or matching placebo in a 1:1 ratio. Subjects will be dosed according to their cirrhosis status (as defined in [Section 9.7.3](#)) and applicable Child-Pugh Score (see [Section 9.7.4](#)) as outlined in [Table 3](#).

Subjects who are non-cirrhotic or classified as Child-Pugh A at screening will receive 5 mg OCA or matching placebo once daily for 3 months. Subjects should titrate to a maximum dose of 10 mg OCA once daily (or matching placebo) at the Month 3 visit or at any study visit following the Month 3 visit based on tolerability of the product and assessment of biochemical response. Up-titration should be considered when ALP and/or total bilirubin are >ULN. A review of safety laboratory results (eg, chemistry, hematology, and coagulation) obtained no more than 2 months prior to the planned up-titration visit must be completed as part of the product tolerability assessment before up-titration can occur (see [Section 7.4.1](#)).

For those subjects that up-titrate to 10 mg, dose may be decreased to 5 mg at any time during the study as considered clinically appropriate (eg, tolerability). Subjects may be titrated back up to a maximum dose of 10 mg once daily based on tolerability and clinical judgment of the Investigator. A review of safety laboratory results obtained within 2 months of the planned up-titration visit date is not required prior to re-challenging a subject up to 10 mg once daily dosing, as long as the decrease in dose/dosing frequency was less than 3 months in duration.

Table 3: Planned Dosing Regimen by Cirrhosis and Child Pugh Score

	Scheduled Dosing Regimen		
	Standard	Modified ^a	
	Non-Cirrhotic/ Child-Pugh A	Child-Pugh B	Child-Pugh C
Starting Dose^b (Day 0)	5 mg daily	5 mg once weekly	5 mg once weekly
Titration 1^c (≥Month 3)	10 mg daily	5 mg twice weekly ^d	5 mg twice weekly ^d
Titration 2^c (≥6 weeks after Titration 1)	NA	10 mg twice weekly ^d	10 mg twice weekly ^d
Titration 3^c (≥6 weeks after Titration 2)	NA	5 mg daily	NA

^a Refer to [Appendix A](#) for additional instructions regarding subjects following the Modified Dosing Regimen.

^b Starting dose based on subject's cirrhosis status and Child-Pugh score at Screening.

^c Planned titration regimen is shown; however, the titration of dose and/or frequency is dependent on subject tolerability, biochemical response, and/or changes in cirrhosis status or Child-Pugh score at any time during the study (see Section 7.4).

^d Dosing per the twice weekly schedule must be at least 3 days apart.

The dosing regimen should be determined as described in Table 4. Investigators should follow the dosing/titration schedule as shown in Table 3.

Table 4: Determination of Dosing Regimen

Cirrhosis?	No	Yes	Yes	Yes
Child-Pugh Score	Any	A	B	C
Dosing Regimen	Standard		Modified for Child-Pugh B	Modified for Child-Pugh C

7.4. Dose Titration Criteria

Dose titration may follow the scheduled dosing regimens described in [Section 7.3](#) or occur due to tolerability concerns or as a result of changes in a subject's cirrhosis status (using histology or non-histological methods as defined in [Section 9.7.3](#) and [Section 9.7.4](#)) or Child-Pugh Score.

Dose titrations may involve increases or decreases in dosing frequency or dose and are dependent on tolerability (as assessed by a review of AEs and safety laboratory results) as well as biochemical response (as assessed by reductions in ALP and/or total bilirubin). In general, down-titration will be done in response to tolerability concerns and can occur at any time while on-study. Up-titration will be done per protocol when subjects have no tolerability concerns and have not achieved an adequate reduction in ALP and/or total bilirubin to within normal limits, or as assessed by the Investigator, or following resolution of a tolerability concern that previously led to down-titration. Up-titrations may only occur to the maximum dose and frequency for each dosing regimen as defined in Section 7.3.

Scheduled Dose Titration - The first dose titration for any subject may occur no earlier than 3 months following initiation of OCA or matching placebo. Subsequent titrations in dose or dosing frequency for subjects following the Modified Dosing Regimens may occur no earlier than 6 weeks (via an unscheduled visit or regular visit- see [Appendix A](#)) following an up-titration.

Tolerability Dose Titration - Investigators may decrease the dosing frequency or dose for any subject at any time during the study, as considered clinically appropriate (eg, tolerability; see [Section 7.4.1](#) and [Section 7.4.2](#)).

Dose Titration due to Change in Cirrhosis or Child-Pugh Score - When subjects demonstrate a change in cirrhosis status (as assessed per [Section 9.7.3](#)) or Child-Pugh Score ([Section 9.7.4](#)), dosing should be reassessed and the dosing regimen modified appropriately. Changes to the dosing regimen are not mandatory and should be based on clinical judgment as well as change in cirrhosis status. Table 5 provides an overview of the possible changes in dosing regimen due to changes in cirrhosis or Child-Pugh Score. Dosing should follow the titration schedule of the new dosing regimen such that the maximum dose within that dosing regimen is ultimately attained, based on tolerability and clinical judgment.

Table 5: Changes in Dosing Regimen Due to Changes in Cirrhosis Status or Child-Pugh Score

Original Status	New Status ^a		
	Non-cirrhotic OR Child-Pugh A	Child-Pugh B	Child-Pugh C
Non-cirrhotic or Child-Pugh A	No Change	10 mg daily → 5 mg daily 5 mg daily → No change or 10 mg twice weekly ^b	5 mg or 10 mg daily → 10 mg twice weekly ^b
Child-Pugh B	5 mg daily → 10 mg daily	No Change	5 mg daily → 10 mg twice weekly ^b 10 mg twice weekly ^b → No change or 5 mg twice weekly 5 mg twice weekly ^b → No change or 5 mg once weekly
Child-Pugh C	10 mg twice weekly → 5 mg daily	10 mg twice weekly → 5 mg daily 5 mg twice weekly → No change or 10 mg twice weekly ^b 5 mg once weekly → 5 mg twice weekly	No Change

^a Once a subject begins dosing with the new dosing regimen, titration should occur as described for that dosing regimen in [Section 7.3](#) or [Appendix A](#).

^b Dosing per the twice weekly schedule must be at least 3 days apart.

Subjects who exhibit development of cirrhosis at any point in the study should be assessed per [Section 9.7.3](#). If the presence of cirrhosis is confirmed and the subject's Child-Pugh score is either B or C, the appropriate modified dosing regimen should be followed. The dose or frequency of investigational product should be down-titrated to the next lowest dosing frequency in the appropriate modified dosing regimen unless the subject is currently taking a dose and frequency also specified in the modified dosing regimen and the Investigator determines that it is clinically appropriate for the subject to continue at that dose ([Appendix A](#)).

Subjects with pre-existing cirrhosis who demonstrate a change in the Child-Pugh Score from A to B or C at any point in the study should also have their dosing modified per the appropriate dosing regimen ([Appendix A](#)).

Subjects who demonstrate an improvement in cirrhosis status or in Child-Pugh Score from B to A, or from Child-Pugh C to B, may be eligible to transition to the standard dosing regimen or the modified dosing for Child-Pugh B, respectively, based on tolerability. Prior to any dosing change, subjects must meet pre-titration assessment requirements for dosing as described in Section 7.4.1.

Child-Pugh Scores will be calculated at all quarterly study visits. All associated visit data (including central laboratory results) should be entered into the eCRF in a timely fashion to confirm that the subject's Child Pugh Score has not changed. If a change in cirrhosis status (as defined in [Section 9.7.3](#)) and/or Child-Pugh Score is observed independent of a study visit, the subject should be contacted via phone to discuss the need for a dosing modification and should be asked to return to the investigative site as soon as possible if a new bottle of investigational product is required to be dispensed.

Subjects' dose and dosing frequency may be titrated up or down within the appropriate dosing regimen based on the calculated Child-Pugh Scores. Up-titration should be done per Investigator discretion and be guided by the pre-titration tolerability assessments.

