To assess the effect of OCA compared to historical controls on liver-related clinical outcomes.
 To characterize the pharmacokinetics of OCA and its conjugates in a subset of subjects.
 To assess health outcomes and pharmacoconomics including cost-effectiveness, resource utilization, and quality of life measures in subjects treated with OCA compared to placebo.
 To assess the safety and tolerability in subjects treated with OCA compared to placebo.

Methodology:

This Phase 4, double-blind, randomized, placebo-controlled, multicenter study will evaluate the effect of OCA on clinical outcomes in subjects with PBC. Subjects will be screened twice during a 1 to 8-week Screening period prior to entering the study to allow for the collection of repeat serum chemistry samples (at least 2 weeks apart) to confirm pretreatment alkaline phosphatase (ALP) and total bilirubin values (refer to Section 9.7.6).

Investigational product will be taken orally, once daily for the majority of subjects; dose and frequency will be modified for subjects with cirrhosis (including subjects progressing to cirrhosis during the study) and classified as Child-Pugh B or C. The randomization will be stratified by ursodeoxycholic acid (UDCA) treatment (yes/no) and baseline bilirubin categories (> upper limit of normal [ULN]/ ≤ ULN).

Schematic Diagram:

EOS = end of study; ULN = upper limit of normal
 Initial dose titration of investigational product should occur at the Month 3 visit, or any study visit thereafter for subjects on all dosing regimens, based on tolerability and biochemical response. Subsequent dose titration(s) for subjects classified as Child-Pugh B or Child-Pugh C and following a modified dosing schedule may occur no earlier than 6 weeks after the previous dose titration.

Dosing frequency will be determined by the presence or absence of cirrhosis and, if cirrhosis is present, by Child-Pugh Score as described below:

- Non-cirrhotic subjects or subjects classified as Child-Pugh A at screening will receive 5-mg OCA or matching placebo once daily for 3 months. Subjects should titrate to a maximum dose of 10-mg OCA once daily (or matching placebo) at the Month 3 visit or at any study visit following the Month 3 visit based on tolerability and biochemical response of the product.

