following review of the pre-titration laboratory results to assess safety and tolerability, the dosing frequency of 5 mg OCA or matching placebo should be increased to twice weekly (at least 3 days apart). Subjects who have maintained the twice weekly dosing frequency for a minimum of at least 6 weeks, and meet the dose titration criteria, should up-titrate to twice weekly dosing with 10 mg OCA or matching placebo. Subjects with at least 6 weeks of twice weekly dosing at 10 mg OCA or matching placebo, and meeting dose titration criteria, should up-titrate to the maximum allowed dose of 5 mg OCA or matching placebo once daily.

Investigators may decrease the dosing frequency (back to once or twice weekly) or dose for any subject at any time during the study, as considered clinically appropriate (eg, tolerability).

Modified Dosing Regimen for Subjects with Child-Pugh C Hepatic Impairment

Subjects with cirrhosis and classified as Child-Pugh C at Screening will follow a modified dosing schedule receiving 5 mg OCA or matching placebo once weekly as described in [Figure 2](#). After a minimum of 3 months dosing once weekly with 5 mg OCA or matching placebo, and following review of the pre-titration laboratory results to assess safety and tolerability, the dosing frequency of 5 mg OCA or matching placebo should be increased to twice weekly (at least three days apart). Subjects who have maintained the twice weekly dosing frequency for a minimum of at least 6 weeks, and meet the dose titration criteria, should up-titrate to the maximum allowed dose of 10 mg OCA or matching placebo twice weekly.

Investigators may decrease the dosing frequency (back to once weekly) or dose for any subject at any time during the study, as considered clinically appropriate (eg, tolerability).

Dose Titration due to Change in Cirrhosis or Child-Pugh Score

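### Protocol Version 3.1 makes regimen changes optional when Child-Pugh class worsens as well as when it improves, contradicting its own synopsis, Section 7.3 and Table 5

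*Protocol*

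**What the plan says.** All references are to Protocol Version 3.1 unless stated.

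- **Section 7.4, change in cirrhosis or Child-Pugh score.** On such a change, "dosing should be reassessed and the dosing regimen modified appropriately". The next sentence reads: "Changes to the dosing regimen are not mandatory and should be based on clinical judgment as well as change in cirrhosis status". Table 5 is then introduced as an overview of possible changes.
- **Appendix A, same topic.** It repeats the optional wording for subjects on a modified regimen. It adds that a transient, explainable laboratory change need not lead to a new regimen, and that the Medical Monitor may be consulted.
- **Synopsis, Methodology.** "dose and frequency will be modified for subjects with cirrhosis (including subjects progressing to cirrhosis during the study") and classified as Child-Pugh B or C.
- **Section 7.3.** Subjects will be dosed by cirrhosis status and applicable Child-Pugh score, as set out in Table 3.
- **Section 7.4, text after Table 5.** A subject with newly confirmed cirrhosis and class B or C should be down-titrated "unless the subject is currently taking a dose and frequency also specified in the modified dosing regimen" and the Investigator judges that dose suitable. Subjects with existing cirrhosis who move from A to B or C "should also have their dosing modified per the appropriate dosing regimen".
- **Dose limits.** Section 7.4: "Up-titrations may only occur to the maximum dose and frequency for each dosing regimen as defined in Section 7.3". Appendix A says that class B subjects "should up-titrate to the maximum allowed dose of 5 mg OCA or matching placebo once daily" and class C subjects "should up-titrate to the maximum allowed dose of 10 mg OCA or matching placebo twice weekly".

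**The concern.** Discretion is right when a subject improves, because nobody need be pushed to a higher dose. Worsening is different: the modified regimens exist to lower the dose in Child-Pugh B and C. The optional sentence covers both directions, so an investigator who leaves a worsening cirrhotic subject on 10 mg daily can cite Section 7.4, while a monitor who objects can cite the synopsis, Section 7.3 and Table 5.

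The explicit limits do not settle the dispute, because they are worded for moves upward. They stop a subject from climbing above the class maximum, but do not bring down a subject who is already above it. What is at stake is consistent dosing across about 170 sites, in the subjects whose liver function is deteriorating. Type I error, power and the 127-event target are not affected.

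**Working it through.** The plan states no figure to reproduce here. The check has three parts.

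**1. Does Table 5 act as a ceiling on worsening?**

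Weekly doses: 10 mg daily = 10 × 7 = 70 mg; 5 mg daily = 5 × 7 = 35; 10 mg twice weekly = 10 × 2 = 20; 5 mg twice weekly = 5 × 2 = 10. The Table 3 maxima are therefore 35 mg/week for class B and 20 for class C.

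| Move | Starting dose (mg/week) | New maximum | Above it? | May stay unchanged? |
|---|---|---|---|---|
| Non-cirrhotic or A to B | 70 | 35 | yes | no |
| Non-cirrhotic or A to B | 35 | 35 | no | yes |
| Non-cirrhotic or A to C | 70 | 20 | yes | no |
| Non-cirrhotic or A to C | 35 | 20 | yes | no |
| B to C | 35 | 20 | yes | no |
| B to C | 20 | 20 | no | yes |
| B to C | 10 | 20 | no | yes |

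All 4 starting doses above the new maximum go down with no option to stay. All 3 within it have that option. The exception in the text after Table 5 draws the same line, and 10 mg daily belongs to neither modified regimen. A general permission to leave the regimen alone cancels both.

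**2. Does another rule bring the dose down?**

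- Section 7.4.1: bilirubin above twice baseline (and above ULN) blocks up-titration, but does not require a reduction.
- Sections 9.7.3.1 and 9.7.4: a change of status requires re-evaluation of the regimen, not a change to it.
- Section 8.4.3.1: raised liver tests lead to repeat testing and clinical follow-up.
- Section 8.4.1.1: product is interrupted for severe drug-induced liver injury. The example given is rising bilirubin or INR not explained by disease progression, so ordinary progression to B or C is the case it is least likely to catch.

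None of these sets a dose ceiling by class.

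**3. How large is the excess?**

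Nominal dose against the class maximum:

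- 10 mg daily kept in B: 70/35 = 2.0
- 10 mg daily kept in C: 70/20 = 3.5
- 5 mg daily kept from B to C: 35/20 = 1.75

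Section 5.5.2.2 treats the liver as the primary site of action and gives modelled liver concentrations of 1.1, 1.5 and 1.7 times normal for A, B and C. Assuming exposure proportional to weekly dose:

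| Change | Dose unchanged | At the new class maximum |
|---|---|---|
| A on 10 mg daily to B | 1.5/1.1 = 1.36 | 1.36 × 35/70 = 0.68 |
| A on 10 mg daily to C | 1.7/1.1 = 1.55 | 1.55 × 20/70 = 0.44 |
| B on 5 mg daily to C | 1.7/1.5 = 1.13 | 1.13 × 20/35 = 0.65 |

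Each figure is relative to the same subject's liver exposure before worsening.

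**The case against.** **The protocol already directs a reduction.** Section 7.3 uses will, the text after Table 5 uses should, and should is this protocol's ordinary verb of instruction. This stands. A reader might infer that Version 3.1 has no dose ceiling for worsening subjects. That goes too far: a ceiling is stated, and one sentence lets a site override it.

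**The synopsis is only a summary.** Its will-be-modified clause mainly contrasts modified with once-daily dosing, and a footnote to its table makes titration depend on tolerability, response and status. This softens the synopsis conflict but leaves those with Section 7.3, Table 5 and the text after it. Table 5 is itself softened by being introduced as possible changes.

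**Discretion has a reason.** The score is calculated at quarterly visits and can move on a passing laboratory value. Warfarin is permitted under Section 9.2, and Table 6 makes no allowance for anticoagulants. An INR above 2.3 scores 3 points where a normal value scores 1, so a total of 5 (class A) becomes 7 (class B) with no hepatic change. This stands and shapes the fix. It does not justify discretion over unexplained worsening.

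**Harm is not shown.** A reader might infer from the 2.0 and 3.5 ratios that subjects would be injured. Section 5.5.2.2 does not support that: it calls the rise in liver exposure modest and reports no apparent effect on overall safety in earlier Child-Pugh B and C subjects with plasma exposure more than 10 times that of healthy subjects. Quarterly scoring, down-titration at any time, repeat testing, the interruption rule and DMC review also reduce the risk.

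**Version 3.1 has been followed by Version 4.** The Version 4 synopsis keeps the will-be-modified wording. Its contents list no longer shows Section 7.4.2 and adds sections on monitoring and interruption for liver chemistries, so this area was reworked. Its Section 7.4 is not available, and the documents do not support saying that the contradiction persists there.

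**Conclusion.** The point holds for Version 3.1 as an internal contradiction. Section 7.4 and Appendix A make regimen changes optional on worsening, while the synopsis, Section 7.3, Table 5 and the text after it call for the dose to follow the new class. A site can rely on the optional sentence to keep a worsening cirrhotic subject at 2.0 (B) or 3.5 (C) times the class maximum by nominal dose. Modelled liver exposure would then be 1.36 or 1.55 times that in class A, instead of 0.68 or 0.44 times at the maximum.

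The exposure figures rest on the protocol's own model and on assumed dose proportionality. The number of subjects affected cannot be estimated from the documents. This is worth correcting because it concerns dosing safety and the correction is cheap, not because injury has been shown.

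**What to change.** In Section 7.4 and Appendix A, confine the optional wording to improvements in class and to transient or explainable changes. Then add:

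> When a subject with confirmed cirrhosis has a worsening to Child-Pugh B or C that is not explained by a transient laboratory change or a non-hepatic cause (eg, anticoagulant effect on INR), the dose must not exceed the Table 3 maximum for that class (B: 5 mg daily; C: 10 mg twice weekly); the Investigator may choose a lower dose.

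The carve-outs are needed. Without them the new rule would collide with the Appendix A exception, and a raised INR from warfarin alone could force a reduction. Table 5 needs no change.

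The cost is a wording change in two places, with no added visits or procedures, and a small loss of investigator discretion to hold a subject above the class maximum. Apply it to Version 4 only if its Section 7.4 or Appendix A still carries the sentence.
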